## 1. Introduction to Application

Not applicable

## 2. Research Plan

### Specific Aims

Service dogs (SDs) is an umbrella term that encompasses a variety of trained dogs which assist individuals with disabilities. The training of these dogs can vary – from highly trained medically-necessitated service dogs to well-trained domestic pets that provide emotional support and comfort to their owners. Although the benefits SDs afford their partners have been examined previously as a means to aid functional tasks, SDs may also provide constant companionship, enhanced feelings of personal safety, and serve as social connections with others.

This proposed three-year, *longitudinal study* will follow individuals with PTSD newly partnered with SDs (SD Group). Participants will be recruited from the Tampa VA catchment. All participants will be asked to complete questionnaire packets at baseline, three, six, nine, twelve, eighteen and twenty-four months after enrolling in the study.

### Research Questions and Hypotheses:

*Specific Aim 1: To determine the impact of service dogs and determine who benefits the most.*

**Hypothesis 1A:** Individuals partnered with SDs will have greater improved mental health over time (Primary outcome will be the PCL checklist. Secondary mental health will be quantified by scores on depression and alcohol use).

**Hypothesis 1B:** Individuals partnered with SDs will have improvements over time in secondary factors of physical, psychosocial, and socioeconomic variables. The secondary factors are defined as follows: 1) physical factors: co-morbidities, medication use, sleep 2) psychosocial factors: community participation, quality of life and 3) socioeconomic factors: demographic and health care utilization and out-of-pocket health care expenses.

*Specific Aim 2: To determine costs associated with total health care utilization and mental health care utilization among Veterans with mental health disorders needs and service or therapy dogs.*

**Hypotheses 2A:** Individuals partnered with SDs will have decreased mental health care utilization over time.

**Hypotheses 2B:** Individuals partnered with SDs will have decreased total health care utilization over time.

*Specific Aim 3: To determine recommendations for providing service dogs to Veterans.*

Develop a strategic plan to provide service dogs to Veterans. A consensus meeting will be planned and will include all investigators of the project along with key individuals from funding agency to discuss findings of study.

*Secondary Aim:* To compare study findings to another VA funded study that is providing dogs as pets to Veterans with PTSD. Both studies are using similar measures to assess mental and psychosocial factors. Data will be compared across groups (SD to dog as a pet) to determine if the highly trained dogs help the Veteran more than having a dog as a pet.

*Projected Time Table*

Training of SDs is time intensive and expensive, with limited numbers of dogs who actually graduate. We will work with vendors to obtain the dogs, but recognize that there may be a significant waiting period prior to pairing. To demonstrate maximum treatment benefits, the data collection phase of this three-year study will be conducted for a minimum 18 months (maximum of 24 months for early enrollees) as we feel the acclimation period for the human-animal bond is longer than 18 months. This allows sufficient time for statistical analyses.

*Timeline*

TASK	YEAR 1				YEAR 2				YEAR 3				YEAR 4				YEAR 5			
	Apr 2011	June 2011	Aug 2011	Oct 2011	Jan 2012	Apr 2012	Aug 2012	Oct 2012	Jan 2013	Apr 2013	Aug 2013	Oct 2013	Jan 2014	Apr 2014	Aug 2014	Oct 2014	Jan 2015	Apr 2015	Aug 2015	Oct 2015
Start up activities, finalize data collection forms, hire and train data collectors	Shaded																			
Renewal training for data collection				Shaded			Shaded													
Advertisement/promotion of study	Shaded	Shaded	Shaded	Shaded																
Recruit participants, collect baseline	Shaded	Shaded	Shaded	Shaded	Shaded															
STUDY HOLD**					Blue	Blue	Blue	Blue	Blue	Blue										
Collect 3-, 6-,9-, 12- 18- and 24-month data on enrolled veterans			Shaded	Shaded	Shaded	Shaded	Shaded	Shaded	Shaded	Shaded	Shaded	Shaded	Shaded	Shaded	Shaded	Shaded	Shaded	Shaded	Shaded	Shaded
Enter data in electronic database and conduct on-going verification			Shaded	Shaded	Shaded	Shaded	Shaded	Shaded	Shaded	Shaded	Shaded	Shaded	Shaded	Shaded	Shaded	Shaded	Shaded	Shaded	Shaded	Shaded
Conduct statistical analyses and summarize findings																				
Apply for additional funding to support follow up work																				
Dissemination of Findings																				
Prepare manuscripts																				Shaded

\*\* Because of ongoing vendor issues, enrollment was stopped for a second time and new vendors have been awarded contracts. Study will extend beyond the three year period utilizing Veterans who signed consent prior to second hold.

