We will be enrolling up to 220 Veterans to be paired with service dogs. The previously cited longitudinal study had only an eight percent attrition rate. Although similar methods are included in this proposal, we recognize that this is a different population; we will plan on a higher attrition rate. Thus, we are estimating a 15 percent drop-out rate ( $n=33$ ), and we will over-recruit participants. Up to two hundred and twenty participants will be recruited over the course of the study. These recruitment numbers are chosen with the expectation that *200 individuals* will complete the study.

A repeated measures design with one fixed effects (any one covariate [TBD]) and 1 within subject effect (time; each subject is measured 5 times [minimum]) achieves approximately 100% power to test the primary fixed effect (dog group status) if a Geisser-Greenhouse Corrected F Test is used with an alpha level=5% and the actual effect  $SD=0.47$  (effect size=5.54). Further, this design achieves approximately 100% power to detect a significant effects among both covariates (alpha level=5%,  $SD=0.8$ ; effect size=5.54) and significant interaction between both the primary fixed effect (dog group status) and each of the covariates (alpha level=5%,  $SD=0.8$ ; effect size=5.54). This analysis assumes a 1st order auto correlation between repeated assessments equal to 0.80.

To assure that we recruit sufficient sample size, we will initiate the following strategies: (1) carefully consider respondent burden when finalizing the baseline survey and interview schedule, (2) employ and train research assistants/data collectors with previous experience in collecting data and who have good communication skills, (3) provide a small reimbursement (\$10.00) for participant time and effort each time a questionnaire is returned, (4) develop posters and recruitment flyers which will be displayed in all mental health clinical areas, and (5) provide in-services on a regular basis to the PTSD and other mental health clinicians explaining the study. These methods have been used successfully in the past by the research team.

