*Screening Visit:* Once a Veteran has agreed to participate in the study, they will be asked to participate in a screening visit. Once the informed consent process is finalized, eligibility criteria will be confirmed. A review of CPRS records will be conducted by the study team to verify the Veteran truly meets all criteria. At this time, if all criteria are met, all baseline questionnaires will be completed and field notes taken. For safety reasons, Veterans who have children younger than 10 years of age in the home for more than 8 hours per day, one day per week or more will be excluded from the study. After 20 dogs have been placed without incident, this criterion will be revisited to potentially allow these Veterans to participate.

- The study team will perform a home evaluation visit prior to referring Veterans to a vendor. This visit will be to ensure the environment is safe and suitable for a

dog. A home environment checklist has been developed and will guide the study team in assessing the environment. An information sheet that provides details to Veterans regarding why and how the home visit will be conducted will be provided to Veterans when Informed Consent is obtained. During the visit, the team will check to see that there is an area for a dog to exercise, relieve itself, sleep, as well as making sure hazardous plants or chemicals are not within reach of a dog. All family members that will be living in the home will be expected to meet with the study team to ensure they understand the study requirements and are on board with bringing a dog into the home. If any issues are identified by the study team during the home evaluation the Veteran will have 3 weeks to fix the issues and reschedule a follow up home evaluation visit. If during the follow up home evaluation the study team determines that the issues are not fully resolved the Veteran will have one additional week to remedy the issues and reschedule a final home evaluation. If the issues remain unresolved the Veteran will be withdrawn from the study. Once the home evaluation has been approved the Veteran will be provided with contact information for the vendor. The Veteran will be instructed to contact the vendor and will be placed on the waiting list. The Veteran will be encouraged to review home owner/rental insurance policy to include a dog and be required to obtain a license for their service dog per local laws.

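### The timeline continues the study with Veterans who consented before the second hold, while the sample section still recruits up to 220 and expects 200 completers; the two are not reconciled, and 200 is not supported

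*Combined protocol and SAP*

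**What the plan says.** **Timeline (under Research Questions and Hypotheses).** The footnote to the chart says: "Because of ongoing vendor issues, enrollment was stopped for a second time and new vendors have been awarded contracts". It continues: "Study will extend beyond the three year period utilizing Veterans who signed consent prior to second hold". In the chart, the row "Recruit participants, collect baseline" is shaded from April 2011 to January 2012, and the advertisement row from April to October 2011. The hold runs from January 2012 to April 2013. Neither recruitment nor advertisement is shaded in the ten columns after the hold. The follow-up data-collection row runs to the last column, October 2015.

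**Design, Sample paragraphs.** The text is in the future tense: "We will be enrolling up to 220 Veterans to be paired with service dogs", and again: "Up to two hundred and twenty participants will be recruited over the course of the study". On attrition, "we are estimating a 15 percent drop-out rate", given as n=33, and the recruitment figure is said to be chosen so that 200 complete. The same section names further VA hospitals as a fallback if enrolment numbers are not met.

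**Not stated anywhere:** how many Veterans had consented before the second hold, whether enrolment re-opened, or whether 220 and 200 were revised after the hold.

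**The concern.** Both statements are current text. The footnote belongs to the operative timeline and is not an amendment log. The Design section describes the present single-group study, since it records that the control group was eliminated. One part of the plan therefore closes recruitment while another still plans it.

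If the footnote governs, the sample is a fixed number that the sponsor already holds, and 220 and 200 are leftovers. If the Sample section governs, the footnote and the chart are wrong. Either way a reader cannot tell who forms the study population or what number of Veterans stands behind the estimated change in PCL and every secondary analysis. The power text does not settle it. The statement under Design gives no sample size, and the one for Hypotheses 1 uses 65 per group in a study that now has one group.

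**Working it through.** **1. The plan's own arithmetic.** Inputs from the Sample paragraphs: enrolment at most 220, drop-out 15%, completers 200.

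- Drop-outs: 0.15 × 220 = 33. This reproduces the stated n=33.
- Completers: 220 − 33 = 187. The stated 200 is not reproduced; the gap is 13, or 13/200 = 6.5%.
- Enrolment needed for 200 at 15% loss: 200/0.85 = 235.3, so 236, which is above the ceiling.
- Loss implied by 220 and 200: 20/220 = 9.1%. At the earlier study's 8% attrition, 200/0.92 = 217.4, so 218. The 220 figure therefore fits the attrition rate that the section says it is not using.

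**2. Completers if the footnote governs.** Let C be the number consented before the second hold, which is not given. Completers = 0.85 × C. With C at most 220, completers are at most 187. Any smaller C lowers this in proportion, but the documents give no basis for choosing a value. The 187 may itself be generous. Veterans can also be withdrawn before pairing, after a failed home evaluation or if still unpaired at 48 months, and the plan does not say whether the 15% covers these losses.

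**3. Precision at the ceiling.** Assumption: a one-group mean change in PCL, with s the SD of the change (not given).

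- 95% half-width = 1.96 × s/√n: 0.139 s at n = 200; 0.143 s at n = 187.
- Change detectable with 80% power at two-sided 5% = (1.960 + 0.842) × s/√n: 0.198 s at n = 200; 0.205 s at n = 187.

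The loss from 200 to 187 is small. The loss from an unknown C cannot be stated.

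**4. Does the printed schedule leave room for new recruits?** The Projected Time Table asks for at least 18 months of data collection and justifies this by the time the human-animal bond takes, so it is read here as time after pairing.

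- Last data-collection column: October 2015.
- Latest pairing for 18 months: about April 2014. For 24 months: about October 2013.
- Version date in the page footer: 26 November 2014. From then to October 2015 is about 11 months.

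A Veteran recruited at the version date would have about 11 months even if paired at once, and the protocol says immediate placement is unlikely. The recruitment contingency cannot yield 18 months of post-pairing data within this chart.

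**The case against.** The strongest reply is that the two statements can both be true. The 220 is a maximum over the whole study and includes those already enrolled, and the footnote does not say that only pre-hold consenters will be used. This stands in part. A reader might infer that the hold left a sample well below 220, or that the stated size is shown not to be delivered because of it. The documents do not support that, because the pre-hold count is missing, and picking illustrative counts and multiplying up standard errors would not supply it.

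The chart is also imperfect evidence. The rows for statistical analysis, funding applications and dissemination have no shading at all, and a second stop implies an earlier stop that is not visible. Blank cells alone prove little. But the footnote makes the point in words, and the recruitment and advertisement rows agree with it.

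Two further inferences should be resisted. The plan to revisit the young-children criterion after 20 placements does not contradict the footnote. Consent precedes confirmation of eligibility, so such Veterans could already have signed. Nor does the hold mean that the only pre-dog measurement is more than a year old, because assessments are repeated every three months until pairing (every six months after 24 months).

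Finally, neither power statement uses 220 or 200. That is true, and it means that nothing else in the plan fixes the sample size.

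**Conclusion.** The concern holds as an unreconciled contradiction together with an unsupported completer figure. The timeline ends recruitment and relies on Veterans already consented; the Sample section still recruits up to 220 and keeps a contingency that the printed schedule cannot accommodate. No shortfall against 220 is shown. The 200 completers fail on the plan's own inputs: at most 187, which is 13 short, even if every one of 220 had consented before the hold. This rests on applying the 15% to all enrolled, as the plan's n=33 does. The effect at the ceiling is slight (√(200/187) = 1.03 on the standard error). What matters is that, if enrolment is closed, the sample size is a known count that the plan omits.

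**What to change.** State in the Sample paragraphs whether enrolment is closed.

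- **If closed:** replace 220 and 200 with the number who had consented before the second hold and the expected numbers paired and completing at the planned 15% loss. Give the single-group precision for mean PCL change at that number, with the assumed SD of change. Remove the contingency to recruit at other hospitals.
- **If re-opened:** correct the timeline footnote, add a recruitment row after the hold, and set an end of data collection that allows at least 18 months of follow-up for the last Veteran paired. Bring 220, 15% and 200 into agreement: either 187 completers, or 236 enrolled.

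The cost is protocol wording, using a count the sponsor already holds in the closed case. The stated size may become less favourable. The re-opened case would lengthen the printed schedule, and keeping 200 completers would mean raising the ceiling by 16.

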### *Background and Significance*

An estimated 16,000 individuals are partnered with SDs today. In the early 2000's, the cost of raising and training these highly skilled dogs, who typically work for eight years, is estimated to range from \$8,500 to \$15,000. Current estimates (from conversations from a variety of vendors) is around \$23,000. Section 2 of Bill H.R. 2792, the Disabled Veterans Service Dog and Health Care Improvement Act of 2001, allows the VA to reimburse costs of SDs and associated training for qualified Veterans. An additional bill was passed in 2010, Bill S.1390, sec 1084 which authorized appropriations to conduct a pilot program on use of service dogs for the treatment or rehabilitation of Veterans with physical or mental injuries or disabilities. This pilot program is to be implemented "120 days after the enactment of this Act, and a three year pilot program to assess the benefits, feasibility and advisability of using service dogs for the treatment or rehabilitation of Veterans with physical or mental injuries or disabilities, including post-traumatic stress disorder (PTSD)" is to be completed. Due to the previous research conducted by the principal investigator (PI) of this proposal, the research team has chosen to focus on PTSD and subsequent mental health improvements which may result from provision of a service dog.

Although some studies have been completed, the research that has been conducted to date has not been designed or controlled in ways that bring us closer to the use of SDs becoming empirically supported treatments. Study samples tended to be small, unrepresentative and heterogeneous, and without adequate control groups. In going forward, of utmost importance is the careful definition of the population under examination and what is to be measured, as well as a need for controlled designs and stated outcomes that are relatively impervious to expectancy and demand effects, and to self-report or personal interest biases. Additionally, most studies have reported on the positive benefits that are observed while in the context of the therapeutic milieu but have not examined whether these effects carry over into other contexts or if they are retained over time. Rigorous efficacy and effectiveness research is needed.

*Background of Service Dogs:* The use of dogs to assist individuals with disabilities began over twenty years ago, and has subsequently flourished. According to the American with Disabilities Act (ADA), if a dog has been individually trained to 'work or perform tasks for the benefit of a person with a disability' it is considered a 'service dog'. Furthermore the ADA defines disability as a 'mental or physical condition which limits major life activity' which would include items such as caring for one's self, walking, seeing, hearing, working, and psychiatric conditions. The dog must be trained specifically to the person's disability. Service animals (including SDs) are legally defined and are not considered 'pets'. International Association of Assistance Dog Partners (IAADP) includes Psychiatric dogs under the umbrella of service animals Therapy animals are not legally defined by federal law. They are typically personal pets of their handlers and work with their handler to provide services to others. Therapy dogs are typically used in facilities or as Animal Adaptive Therapy. Various service dog agencies, though train dogs to be companions to individuals with mental health disabilities and refer to them by a variety of names including skilled companion dog, special needs therapy dogs, and

social/therapy dogs. Presently an estimated 16,000 individuals use a SD for mobility related impairments. As limited research exists, the characteristics of this group are relatively unknown, including the distribution of disabilities and demographics of the population. Depending on the type of service dog, various aids are provided. For example, mobility SDs provide aid with mobility-enhancing and energy-saving tasks: pulling wheelchairs, assist with transfers, open doors, turn light-switches on and off, and retrieving objects (e.g., telephone, towels, clothing). Psychiatric service dogs provide aid in assistance of a medical crisis, treatment related assistance, assistance coping with emotional overload, and security enhancement tasks.

Additional sections of this background focus on research that currently exists which justifies why we are examining certain outcomes. The remainder of the background section is divided into four sections encompassing 1) Mental Health and PTSD, 2) Mental Health and Service Dogs 3) Service dog impacts on secondary factors: Physical, Psychosocial, Economic and 4) Service dogs and Healthcare Utilization.

*Mental Health and PTSD:* Epidemiological studies with civilian populations, including the largest of which is the National Co-morbidity Survey-Replication (NCR-S), show that the lifetime prevalence of PTSD is 6.8% in the United states, with women outnumbering men almost 3-to-1 (9.7% women, 3.4% men). Surveys of base rates for PTSD in military personnel returning from wars in Iraq and Afghanistan have yielded a wide range of estimates. Rates have varied considerably, but large, convenience samples of deployed veterans have in general ranged between 5-20% for PTSD in non-treatment seeking veterans, while studies looking at veterans who are seeking treatment report rates as high as 50% for veterans who screen positive for PTSD.

*The Use of the Diagnostic Interviews and Instruments in PTSD Studies:* The diagnosis of PTSD is reached when a trained clinician determines that the criterion for the disorder has been met according to agreed- upon symptoms. To aid in the reliable diagnosis of a psychiatric disorder structured clinical interviews have been developed which allow for increased agreement upon the classification of a diagnosis. The Clinician-Administered PTSD Scale (CAPS) has become the gold standard for classification and determination of PTSD in trauma populations. It has been well validated has been used in hundreds of studies.

Methods to screen for PTSD, as used in the above studies on prevalence, can vary from as little as a few items (e.g. 4 items on the PC-PTSD, to the 17 items on the PTSD Checklist (PCL) which directly relate to the symptoms needed for diagnosis). The screening instruments are extremely valuable, particularly when time, limited resources, or costs are factors that will not allow for a face to face clinical interview to be conducted. All such screening instruments are judged against the gold standard of the CAPS in determining how well they approach agreement in the reporting of symptoms or stating there is a case of PTSD present. While all screening instruments vary somewhat from the highest standard of the structured clinical interview, the PCL has been found to be a well validated and reliable instrument when assessing symptoms of PTSD across time.

In addition to PTSD, common co-morbid psychiatric conditions can frequently occur. Vietnam Veterans have most commonly reported problems with depression, anxiety, and alcohol, among Veterans who had high levels of war-zone exposure being significantly more likely than those with low exposure to develop the disorders. Depression and alcohol problems have continued to be common among returning Veterans, with rates ranging from 14% to 27%. A related study, evaluating mental health problems among 88,235 US soldiers returning from Iraq, showed that 20.3% of active and 42.4% of reserve soldiers required mental health treatment, including treatment for alcohol problems, and that many reported a fourfold increase in concern about interpersonal conflict in a period of 3 months post-deployment, namely with family and significant others.

*Mental Health and Service Dogs:* Animal-Assisted Therapy (AAT), a form of SD, has been associated with a positive influence on individuals with psychiatric symptoms. Recent work by Anonioli et al, demonstrated that subjects with depression randomized to interaction with dolphins (vs. no dolphin interaction) demonstrated significantly decreased depression scores following exposure. Columbo et al. demonstrated that among three groups of the institutionalized elderly, the group randomized to animal therapy demonstrated significant increased quality of life and decreased symptomology. Berget et al. demonstrated in a randomized trial involving exposure to farm animals (vs. no exposure) among subjects with schizophrenia, anxiety disorder and affective disorders, the exposed group demonstrated significantly increased self-efficacy scores and quality of life scores.

Although research exists to document that depression is at increased levels in disabled population compared to that of the general population, little of the SD research has assessed level of depression in study participants. Findings from previous grants conducted by the PI have shown that receipt of SDs, positively impacts the occurrence of depression. In addition, Rintala et al. found individuals newly partnered with SDs to exhibit modest improvements in depressive symptoms over a 6-month period of time. **Our study will use the PCL checklist as the main outcome and include measures of depression and alcohol use as additional primary outcomes. (Hypotheses 1A).**

*Service dog impacts on secondary factors: Physical and Psychosocial:* In the studies that have been completed to date on the use of SDs, the impact that SDs have on psychosocial outcomes have been examined at length. Most of the research conducted, has been completed on individuals who are using wheelchair SDs opposed to therapy dogs.

Physical: A similar relationship has been found for individuals who have PTSD. In a recent sample of OEF/OIF veterans, a substantial number of Veterans who develop PTSD often have co-morbid chronic pain. One recent sample found that approximately 35% of chronic pain patients carry a diagnosis of PTSD, while in a study of patients with low back pain, 51% of the patients evidenced significant PTSD symptoms. A strong association has been found between the occurrence of pain, and problems with emotional and physical functioning in the returning OEF/OIF Veteran population. There is a strong need to consider how these factors impact overall functioning and how treatments, including medical and psychotropic medication are utilized.

There have been a number of studies, on Veterans with PTSD which have reported poorer physical health, increased medical utilization, and greater work impairment than those without PTSD. Other studies in a civilian female population found that the presence of PTSD accounts for significant functional impairment, beyond that of the physical aspect of the trauma. This was evident on measures of physical functioning, vitality social functioning and role limitations, with similar results in decreased general health, vitality and social functioning in patients who still met criteria for PTSD, one year after enduring physical traumas that required hospitalizations and surgery. These findings highlight the association between trauma, presence of PTSD and greater functional impairments, which is often present in our Veteran population.

Psychosocial: Several studies have examined changes in self-esteem of individuals partnered with SDs. Rintala et al. found new SD partners (n=16) exhibited significant increases in self-esteem. In a cross-sectional survey of SD partners (n=202) conducted by Fairman et al., 4 participants self-reported increased self-esteem, confidence, safety and independence as well as better coping abilities.

Individuals with disabilities are less likely to be able to fully participate in their communities., Excessive time spent in self-care and medical needs can limit the availability of, and energy to pursue, social and leisure activities. Eddy et al. observed the public's behavior toward individuals using wheelchairs with and without their SDs. Significantly increased numbers of passerby smiles and initiated conversations were seen when the SD was present compared to when the dog was not present. These results were noted first with children and then with adults using wheelchairs in a variety of settings. Assistance animals serve as social buffers by alleviating discomfort and awkwardness according to these studies.

